## 7. STUDY INTERVENTION

### 7.1 Description of all Trial Periods

#### 7.1.1. Enrollment visit

During the enrollment visit, medical history data and clinical symptoms of the respiratory system will be collected from an interview. A physical examination, Vignos scale (VS) assessment, Brooke scale (BS) assessment, and spirometry (Jaeger, Germany), Respiratory muscle assessment (Maximal inspiratory pressure -MIP, and Maximal expiratory pressure- MEP), Assessment of the muscles of the upper limb (Performance of Upper Limb -PUL), Maximal grip strength (dynamometry) will be performed in all participants.

**Participants on arm 1 and 2 will receive an electronic individual spirometer (AioCare) with a 2-h training session how to use it. Each participant was then asked to perform on their own three correct spirometry measurements twice daily (morning and evening) at home.**

**Participants from arm 2 and 3 will receive a 1-hour training with respiratory rehabilitation and link to video presentation with respiratory rehabilitation exercises to home daily using.**

- Functional status

The functional status of the participants was assessed by the Vignos scale (VS). The scores on the VS range from 1 to 10 (1 - the subject can walk and climb stairs without assistance, 10 - the subject is

confined to a bed). The VS allows staging of the disease and focuses on functional ambulatory activities. This is the main scale used for characterizing the progression of disease [12]. Upper limb functional status was assessed with the 6-point Brooke scale (BS) (1 - the subject can abduct their arms in a full circle until they touch above their head, 6 - the subject has no useful function of the hands) [13].

- Respiratory muscle assessment

MicroRPM- Maximal respiratory pressure and reflecting respiratory muscle strength was measured using a calibrated portable hand-held mouth pressure meter (MicroRPM; Micro Medical Ltd., Rochester, England) in a sitting position. To measure maximal expiratory pressure (MEP), subjects performed maximal expiratory effort after maximal inspiration. Maximal inspiratory pressure (MIP) was measured by exerting maximal inspiratory effort after maximal expiration. To measure these pressures, effort was maintained for at least 1 second. The highest positive MEP value and the lowest negative MIP value in three or more attempts were chosen. We calculated percent predicted MEP (MEP%) and MIP (MIP%) values according to the formulas: **MEP%**  $MEP * 100 / (7.619 + (7.806 * age) + (0.004 * height * weight))$ ; **MIP%**  $MIP * 100 / (-27.020 - (4.132 * age) - (0.003 * height * weight))$

- Pulmonary function tests

Lung function by spirometry using the calibrated, computerized spirometer Pneumo Screen (Jaeger, Germany) will be performed according to the European Respiratory Society and American Thoracic Society recommendations, by a certificated, experienced pediatric pulmonologist [6,14]. The highest value of forced vital capacity (FVC), forced expiratory volume in 1 second (FEV1), peak expiratory flow (PEF) expressed as liters (L) and liters per minute (L/min) accordingly, and percent predicted value (%pv) from correct acceptable attempts will be evaluated. The results will be compared with results from home electronic spirometry.

- Assessment of the muscles of the upper limb

Performance of Upper Limb (PUL)- a functional scale specifically designed for assessing upper limb function in Duchenne muscular dystrophy (DMD). It includes three domains (shoulder, mid- and distal), each including items exploring activities easily related to activities of daily living that both patients and clinicians identified as relevant. Each dimension (shoulder, mid, distal) can be scored separately. In the PUL 2.0 there is a maximum score of 12 for the shoulder level, 17 for the mid-level, and 13 for the distal level. A total score of 42 can be achieved by adding the three level scores [15].

Dynamometry – Maximal grip strength was measured using dynamometer FT-5988 – N1 (Spais, Poland) – very sensitive electronic device developed to measure grip in very weak patients, the device can be also applied in assessment of healthy subjects. The dynamometer measures forces from 0 to 1000N with a resolution of 0,02N. All measurements were conducted by the same experienced and trained evaluators. Grip strength was measured on the dominant side with a high precision dynamometer. All tests were performed with patients seated on a chair or in their wheelchair facing a table with the forearm placed on the table on the waist level. Trials were carried out with strong verbal encouragement asking the patients to provide maximal voluntary isometric contractions for 3 s. A rest period of about 30 s was respected between the trials. Patients were asked to perform three trials. The mean value was calculated from three valid trials.

- Telerehabilitation – respiratory exercises

Participants from arm 2, and 3 will receive a 1-hour training with respiratory rehabilitation and link to video presentation with respiratory rehabilitation exercises to home daily using.

The video with the instruction of respiratory exercises: positive inspiratory pressure, glossopharyngeal breathing and positive expiratory pressure was shown to parents and patients at the Conference during the Physical Therapy panel. Participants were asked to perform the exercises themselves at home without physiotherapists' assistance. Patients were encouraged to train every day, three times a day. On the video patients received following instructions:

1. Breath stacking (positive inspiratory pressure): patients were asked to take maximal inhale, then without exhaling, to take another 1-3 inhaled, and hold for 5 seconds. Boys were instructed to repeat the exercise 5 times. The aim of the exercise was to increase lung volume. The same exercise was presented with the use of balloon – inflated balloon – patients were instructed to inhale the air from balloon, without exhaling and try to hold as much air in the lungs as possible – hold for 5 seconds and repeat for 5 times.
2. Glossopharyngeal breathing – patients were instructed to push series of small volumes of air by tongue and pharynx into the lungs by saying 'cat' in Polish - patients were encouraged to repeat the exercise for 5 times.
3. Positive expiratory pressure – inflating the balloon – patients were instructed to inflate the balloon by inhaling by nose and exhaling by mouth – the exercise should be repeated for 3 times. Caregivers were encouraged to try different types of balloons to find optimal elasticity of material (optimal resistance). The video is available in the internet <https://www.youtube.com/watch?v=AEaxOsuJimU&feature=youtu.be>.

**7.1.2 Follow-up visit**

**Visit 1**

- Feasibility home e- monitoring pulmonary function survey

Participants from arm 1 and 2 during visit 1 (after 4 weeks training home using e-device), will be completed a survey that included questions about home spirometry (compliance, satisfaction, and problems with the use of the electronic spirometer at home). Patients were asked to express their general satisfaction and the intelligibility of the instructions from the AioCare home spirometry on a 5-point scale, where "1" meant the worst and "5" meant the best score. Participants who were not able to perform spirometric measurements regularly were also asked the reason why and what would help them to take measurements more regularly. The last question concerned the benefits of home spirometry (table 1).

Table 1. Survey of satisfaction and possibility of home e-monitoring pulmonary function in DMD patients.

Home AioCare e-spirometry				
1. Mark on the scale how you rate the monitoring of lung function with the home spirometer.				
1	2	3	4	5

the worst					the best	
2. Mark on the scale how you assess the comprehensibility of the instructions received for self-measurements of spirometry.						
1	2	3	4	5		
the worst					the best	
3. If you have not been able to perform spirometric measurements regularly, what was the most common reason for this?						
- Correct blowing into the spirometer is too difficult for me						
- I don't have time to blow into the spirometer						
- I have no motivation for this assessment						
- I feel unwell						
- I forget to take the measurements						
- other reasons: .....						
4. What would be helpful for you to take measurements every day?						
- reminder sent via SMS						
- weekly online appointment with your doctor						
- weekly report of my results with interpretation						
- I am not able to take measurements everyday						
- other: .....						
5. Do you think that you benefit from home spirometry measurements?						
YES NO						
6. If 'YES', the benefits are:						
- I can breathe easier						
- I can clear my lungs easier						
- I feel more confident						
- I like to use new electronic spirometer						
- I will not be afraid of performing spirometry in the hospital						
- other: .....						

- Feasibility telerehabilitation

The structured questionnaire consisted of questions that covered several areas: (1) respiratory exercises; (2) additional information required with respect to exercises and home-based program; (3) satisfaction from program.

Respiratory exercises: The participants were asked: (a) whether the exercises were performed (yes/no, alone/with assistance), (b) possibility to implement this treatment to daily routine and about how often the exercises could be performed from patients perspective (3 times daily/ 1-2daily/ few times a week/not possible), (c) difficulty of the exercises (all exercises possible to perform/ possible to perform after practicing/some exercises too difficult, all exercises too difficult).

Additional information: The caregivers were invited to leave an e-mail contact in case they needed expanded individual consultation or training.

Satisfaction from program: Respondents were also asked to assess general satisfaction, appropriateness of the exercises and intelligibility in six points scale, where 0 meant the worse and 5 meant the best score.

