### **3. AIMS, OBJECTIVE**

**Objectives:**

The primary objective of this study is to evaluate whether using home electronic device to monitoring pulmonary function and/or home telerehabilitation can slow the rate of progression pulmonary function in males with DMD compared to control group without using home e-device and telerehabilitation.

The second aim of this study is:

to investigate whether it is possible to monitor pulmonary function at home using an electronic spirometry system called AioCare in boys with DMD.

to assess the acceptance of telerehabilitation of respiratory system in this group of patients.

to assess the acceptance of electronic home monitoring of respiratory system in this group of patients.

to assessment of the quality of life of patients subjected to electronic monitoring and pulmonary rehabilitation vs. not subjected (validated questionnaires)

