## 4. STUDY DESIGN

### 4.1 Overall design

The study consists of 4 arms: 3 actives and 1 control (figure 1).

ARM 1: Patients in arm 1 use electronic home device to measurements pulmonary function,

ARM 2: Patients in arm 2 use electronic home device to measurements pulmonary function, and perform telerehabilitation,

ARM 3: Patients in arm 3 perform telerehabilitation

CONTROL GROUP: Patients without home e-monitoring pulmonary function and telerehabilitation.

Enrolment of a patient to one of four groups (active or control) takes place after enrolment visit in random order.

As a part of the clinical trial, diagnostic examinations evaluating progression of the disease, pulmonary function tests will be performed periodically. The compliance, efficacy, accomplishment in all patients will be monitored by questionnaire during follow-up visits. The problems with investigate procedures (e-spirometry, telerehabilitation) and patients' personal well-being will be controlled using telemedicine technologies. Additional visits in the research center will be provided if any adverse events occur. This model will be continued for 12 months from the enrolment. After 4 weeks the first home e-monitoring pulmonary function and respiratory telerehabilitation efficiency analysis will be performed.

The study may be continued for 12 months or in case of negative impact of the intervention on patients' health and well-being, terminated with further patients monitoring

[figure not shown]

Figure 1. Study design

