### 4.2.2 Home respiratory telerehabilitation

A module with exercises for training respiratory muscles, will be included in an additional smartphone application.

It will be a series of 4 exercises aimed at strengthening respiratory muscles, to be performed after the spirometry test; twice every day.

Participants will perform forced exhalation exercises with a relaxed epiglottis, exercises to improve the mechanics of the chest and the mobility of the shoulder girdle. The duration of the exercises is approximately 7 minutes. The exercise program will be recorded in the form of an instructional video.

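### The Visit 1 telerehabilitation item puts once and twice daily in one answer, so it can be read against one of the protocol's two stated exercise frequencies but not the other

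*Protocol*

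**What the plan says.** Section 4.2.2 of the protocol, which describes the telerehabilitation procedure, sets the frequency: "It will be a series of 4 exercises aimed at strengthening respiratory muscles, to be performed after the spirometry test; twice every day".

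Section 7.1.1, which describes the exercise video, gives another: "Patients were encouraged to train every day, three times a day".

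The telerehabilitation questionnaire under Visit 1 (section 7.1.2) has an item on fitting the exercises into the daily routine. It asks "how often the exercises could be performed from patients perspective (3 times daily/ 1-2daily/ few times a week/not possible". The companion item on performance asks "whether the exercises were performed (yes/no, alone/with assistance", which carries no frequency. Difficulty and satisfaction are asked separately.

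The questionnaire serves a secondary aim in section 3: "to assess the acceptance of telerehabilitation of respiratory system in this group of patients". Section 4.1 says of follow-up generally: "The compliance, efficacy, accomplishment in all patients will be monitored by questionnaire during follow-up visits".

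**The concern.** A boy who could do exactly what section 4.2.2 describes has to tick the same answer as a boy who could manage one session a day, which is half of it. If section 4.2.2 gives the intended frequency, the item cannot separate boys who find the programme workable from boys who do not, at the level that matters most.

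The gap arises at data collection. Once the two frequencies share a box, no analysis plan can pull them apart. Nothing else described would fill the gap: the performance item is yes or no, the later visits list no further rehabilitation questionnaire, and section 4.2.2 mentions a smartphone application without describing any usage log.

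At stake is how clearly the trial can say that boys and families find the programme feasible at its stated frequency.

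**Working it through.** The plan gives no figure to reproduce here, so the check maps each answer onto the protocol's two stated frequencies.

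**Inputs**
- Frequency in section 4.2.2: 2 sessions a day.
- Frequency in section 7.1.1: 3 sessions a day.
- Four answer options in the Visit 1 item.
- Telerehabilitation arms as numbered in section 4.1: arms 2 and 3, planned at 50 boys each, so 2 × 50 = 100.

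**Step 1: score each answer against each frequency.** An answer is ambiguous if it covers frequencies both at or above the target and below it.

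| Answer | Sessions a day covered | Against 2 a day | Against 3 a day |
|---|---|---|---|
| Three times daily | 3 | meets | meets |
| One to two daily | 1 or 2 | cannot be told | below |
| A few times a week | under 1 | below | below |
| Not possible | 0 | below | below |

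Only one cell is ambiguous, and it is where the boy who could do exactly two sessions falls.

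**Step 2: what can be learned.** Let a be the share ticking three times daily, q the share ticking the merged answer, and f the unknown fraction of the merged group who could manage two sessions.
- Share able to do at least 3 a day = a, which is known.
- Share able to do at least 2 a day = a + f × q, with f anywhere from 0 to 1. It therefore lies between a and a + q, a band of width q.

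**Step 3: size.** The documents give no value for q. Taking 20, 30 and 40% purely as assumptions, the band is 20, 30 or 40 percentage points wide. If nobody ticks the merged answer, the width is zero. For scale, the largest sampling standard error of a proportion with 100 boys is √(0.5 × 0.5 / 100) = 0.05, or 5 points. Recruiting more boys shrinks that standard error but leaves the band unchanged.

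**Step 4: after splitting the merged answer.** Against 2 a day, twice daily meets and once daily is below. Against 3 a day, both are below. No ambiguous cell remains under either frequency.

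**The case against.** The strongest reply is that the item was built around three sessions a day. Its top option matches section 7.1.1, and against that frequency it has no flaw. On this view the real defect is the contradiction between sections 4.2.2 and 7.1.1, and aligning the answers is a consequential edit. Much of this stands: the difficulty arises only if two a day is the intended frequency, and the two sections must be reconciled in any case. But reconciling them does not by itself repair the item. If section 4.2.2 is the one that stands, the answer list still fails.

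Second, the protocol sets no threshold for meeting or missing a frequency on this item and does not plan to report a share at or above two a day. It asks for the patient's own view, for which coarse categories can be adequate. This also stands, and it keeps the severity low.

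Third, the questionnaire is described in prose and the printed form is not shown, so its final wording cannot be checked. That is fair. The point applies to the options as the protocol lists them.

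A reader might go further and infer three things that the documents do not support:
- That the acceptance aim cannot be answered. It can still be addressed through the items on performance, difficulty and satisfaction.
- That adherence is mismeasured or the FVC comparison is affected. The item asks how often the exercises could be done, not how often they were done, and the FVC comparison does not depend on it.
- That a loss of 20 to 40 points has been shown. That range is an assumption about q, and the true value could be small.

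**Conclusion.** The point holds in a limited form. The protocol states two exercise frequencies that must be reconciled, and the Visit 1 item can be read cleanly against only one of them. Against "to be performed after the spirometry test; twice every day", boys who could do the whole programme and boys who could do half of it share an answer. The share finding two sessions a day feasible is then known only within a band equal to the share choosing that answer, whose size the documents do not give.

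This rests on two conditions: that the printed form uses the options listed in the protocol, and that no exercise log exists beyond what is described. Severity is low. The effect is on the interpretation of perceived feasibility, one part of a secondary aim.

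**What to change.** Reconcile sections 4.2.2 and 7.1.1 on the number of daily sessions; which figure is intended is for the sponsor to confirm. In the Visit 1 telerehabilitation questionnaire, replace the merged answer with two: twice daily and once daily. The list then has five options: three times daily, twice daily, once daily, a few times a week, and not possible. Report the full distribution of answers, so that it can be read against whichever frequency is confirmed.

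The split need not wait for the reconciliation, since the five options score cleanly either way. The cost is one extra tick box, with no added visit, procedure or staff. The downside is that answers already collected with the merged box can be reported only as the merged category. If both forms end up in use, a table over all boys would have to combine the two new answers.

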### **Visit 2 and Visit 3**

All patients will be followed up after 3, and 6 months from visit 1. Lung function testing, will be recorded and assessed at this visit.

Lung function by spirometry using the calibrated, computerized spirometer Pneumo Screen (Jaeger, Germany) will be performed according to the European Respiratory Society and American Thoracic Society recommendations, by a certificated, experienced pediatric pulmonologist [6,14]. The highest value of forced vital capacity (FVC), forced expiratory volume in 1 second (FEV1), peak expiratory flow (PEF) expressed as liters (L) and liters per minute (L/min) accordingly, and percent predicted value (%pv) from correct acceptable attempts will be evaluated. The results will be compared with results from home electronic spirometry.

### **End -point visit**

- During the end-point visit (after 12 months), medical history data, clinical symptoms of the respiratory system will be collected from an interview. A physical examination, Vignos scale (VS) assessment, Brooke scale (BS) assessment, and spirometry (Jaeger, Germany), Respiratory muscle assessment (Maximal inspiratory pressure -MIP, and Maximal expiratory pressure-MEP), Assessment of the muscles of the upper limb (Performance of Upper Limb -PUL), Maximal grip strength (dynamometry) will be performed in all participants.

## **8. STATISTICAL CONSIDERATIONS**

### **Sample size estimation**

Estimation of the sample size was based on the expected differences of the FVC between the groups with and without intervention. In the reference studies annual decline of FVC is varied between 6-11% (mean 8.5%). Assuming that telerehabilitation with using mobile spirometry can decrease this decline to 6% per year with standard deviation of 3% we estimated sample size for the study arms. Taking into account 80% power of the test, 5% significant level, the number of the subjects in the arm 1 (AioCare

device spirometry + telerehabilitation of the respiratory system) and control group equals 46 per group; finally 50 subjects per group were established. The same number of subjects were determined in the rest arms of the study (arm 2 – only mobile spirometry and arm 3 – only telerehabilitation).

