**Study Description:**

The controlled and observational 12-months study with prospective cohort design and longitudinal data collection performs in paediatric patients with established diagnosis of DMD, at the Department of Allergy and Pulmonology Medical University of Gdansk, Poland.

The study includes 200 patients with DMD diagnosis confirmed by genetic testing, 7-17 years old (7  $\geq$  and  $<$ 18) at the study entry with the routine standardized a follow-up of up to 4 weeks, 12 weeks, 24 weeks and 12 months.

The study size is estimated at 200, with a dropout rate after the 12-month follow-up period being ca. 10% (N=180). The study consists of 4 arms: 3 actives and 1 control (each arm of n=50 participants; with dropout rate after 12 months ca.10%, n=45).

Duration of the project March 2021 - March 2025.

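### The stated 46 per group does not follow from the printed inputs, which need 23 to 24 per group for 80% power

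*Protocol*

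**What the plan says.** All the inputs and the result stand in one paragraph, Sample size estimation in Section 8 of the protocol.

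- Control decline: "In the reference studies annual decline of FVC is varied between 6-11% (mean 8.5"%).
- Effect and variability: the combined intervention "can decrease this decline to 6% per year with standard deviation of 3% we estimated sample size for the study arms".
- Error rates: "Taking into account 80% power of the test, 5% significant level".
- Result, for the arm with both components against control: "device spirometry + telerehabilitation of the respiratory system) and control group equals 46 per group; finally 50 subjects per group were established". The same number is then applied to the two single-component arms.

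The Study Description in the synopsis gives the expected attrition: "each arm of n=50 participants; with dropout rate after 12 months ca.10%, n=45". The sample-size paragraph does not state sidedness, an adjustment for multiple comparisons, a separate control-arm SD or an inflation for a non-parametric test.

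**The concern.** A difference of 2.5 points against an SD of 3 is a large standardised effect (0.83), and 46 per group is far more than 80% power needs for it. At least one of the printed figures is therefore wrong, or an input is missing.

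This calculation is the protocol's only justification for 50 per arm and 200 boys in all, and it concerns the comparison behind the primary objective. As written, a reader cannot tell whether combined intervention against control has about 97% power or about 79%. If SD 3% is right, the protocol asks for about twice the patients that 80% power requires, and a null result would be read as weaker evidence than it is. If another SD was used, the variability assumption against which a null result would be judged is misprinted, and the expected completers fall slightly short of the power claimed.

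Separately, the protocol's own completer count (45) is below its own stated requirement (46).

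**Working it through.** **Inputs.** From Section 8: control decline 8.5%, intervention decline 6%, so a difference of 2.5 points; SD 3; power 80%; significance level 5%. From the Study Description: 50 per arm, about 10% dropout, 45 completers. Assumed, because not stated: a two-sided test and the same SD in both arms.

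**Attempt to reproduce 46.** Normal approximation for two means:

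n per group = 2 × (1.960 + 0.842)² × (SD / difference)² = 2 × 7.85 × (3 / 2.5)² = 22.6, so **23**.

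The noncentral t calculation with standardised difference 2.5 / 3 = 0.833 gives 23.6, so **24**. The stated 46 is not reproduced.

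**Power on the printed inputs (two-sided t-test).**

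| n per group | Power |
|---|---|
| 24 | 80.7% |
| 45 (expected completers) | 97.4% |
| 46 (stated requirement) | 97.7% |
| 50 (enrolled) | 98.5% |

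**Other readings at 80% power, SD 3.**

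| Variant | n per group |
|---|---|
| One-sided 5% | 18 to 19 |
| Wilcoxon, efficiency 0.955 or 0.864 | 25 to 28 |
| Bonferroni, 3 / 4 / 6 comparisons | 32 / 34 / 37 |
| Four-arm F-test, several assumed patterns of means | about 17 to 33 |

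None comes near 46.

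**What does give 46.**

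- A two-group total: 2 × 23 = 46, printed as a per-group number.
- SD = 3 × √2 = 4.24: 2 × 7.85 × (4.24 / 2.5)² = 45.2, so 46 (the t-test gives 46.2).
- SD 3 in the treated arm and about 5.2 in controls: (3² + 5.2²) × 7.85 / 2.5² = 36.04 × 7.85 / 6.25 = 45.3, so 46.

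**Dropout.** 50 × 0.9 = 45, one below 46. Keeping 46 after 10% loss would take 46 / 0.9 = 51.1, so 52 enrolled. If 24 is the true requirement, 24 / 0.9 = 26.7, so 27 enrolled would do.

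**Power at 45 if SD is 4.24.** 78.9% by the t-test and 79.8% by the normal approximation. For comparison, 46 per group gives 79.8% by the t-test.

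**The case against.** The strongest reply is that a common SD is the reader's assumption. Grammatically, the 3% attaches to the decline under intervention, and no control-arm SD is printed. With a control SD of about 5.2%, 46 follows and the 3% is not wrong. That is a possible history of the number, and it stands as a third explanation. It does not rescue the paragraph, because an input that determines the result would then be missing and the figure still could not be reproduced from what is written.

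A second reply is that the error is conservative. On the printed inputs the comparison has ample power, and the shortfall under SD 4.24% is about one percentage point. This is correct. The fault is a justification that is false as written; enrolment is not shown to be too small.

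Third, the dropout mismatch is slight. It is one patient per arm, the rate is given only as approximate (8% loss would leave exactly 46), and the point disappears if 24 suffices. It is fair to treat it as secondary. It remains true that the protocol's two sections disagree, and that under SD 4.24% power at 45 is below 80% by either method.

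**Conclusion.** The concern holds. Assuming a two-sided test and a common SD of 3 percentage points, the printed inputs require 23 (normal) or 24 (t-test) per group against 46 stated, and 46 per group gives 97.7% power against 80% stated. A one-sided test would widen the gap, and none of the adjustments tried at 80% power closes it.

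The protocol does not reveal whether the n, the SD or an omitted control-arm SD is at fault, and this review does not claim to know. A statistical analysis plan could not settle it by adding detail, because the protocol states both the inputs and the result, and they disagree. The 45-versus-46 mismatch is real but minor.

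**What to change.** Rewrite the sample-size paragraph so that inputs, n and power agree. State the SD for each arm, the test and its sidedness, and give power at the 45 completers in the Study Description. The wording depends on what was actually used:

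- **SD 3% in both arms:** keep 50 per arm, say that 24 per group suffices for 80% power, and that 45 completers give about 97%.
- **SD about 4.24%:** print that SD in place of 3%, and say that 45 completers give about 79%.
- **A larger control-arm SD:** print it, and recompute power at 45 completers from both SDs.

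The cost is protocol wording only. No patients are added, and no arm, endpoint or analysis changes.

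### Do the swapped arm numbers in the sample size section change which comparison the trial is sized for?

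*Protocol*

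**What the plan says.** Section 4.1 (Overall design) defines the three active arms by number. The first has the home spirometer and nothing more: "ARM 1: Patients in arm 1 use electronic home device to measurements pulmonary function". The second adds the exercises to the spirometer: "ARM 2: Patients in arm 2 use electronic home device to measurements pulmonary function, and perform telerehabilitation". The third has the exercises without the spirometer, and the fourth group is a control with neither component.

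Section 7.1.1 (Enrollment visit) delivers the interventions by number. For the device it says "Participants on arm 1 and 2 will receive an electronic individual spirometer (AioCare". The rehabilitation training and the link to the exercise video go to arms 2 and 3, and the telerehabilitation paragraph of the same section repeats this. At Visit 1, Section 7.1.2 gives the home spirometry survey to arms 1 and 2.

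Section 8 (Sample size estimation) states one effect: "Assuming that telerehabilitation with using mobile spirometry can decrease this decline to 6% per year with standard deviation of 3" percent, against a mean decline of 8.5% per year in the reference studies. At 80% power and a 5% level it then sizes the arm that it numbers 1 against control. The bracket after that number describes the arm as AioCare "device spirometry + telerehabilitation of the respiratory system) and control group equals 46 per group", a figure later rounded up to 50. The same size is given to "the rest arms of the study (arm 2 – only mobile spirometry and arm 3 – only telerehabilitation".

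**The concern.** Section 8 attaches the number 1 to the combination and the number 2 to spirometry alone, which reverses Section 4.1. It is also the only statistical text in the protocol that numbers the arms, and the only place where a specific contrast with control is given an effect, a power and a significance level.

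Someone who took the sized comparison from Section 8 as arm 1 against control, and applied it to data coded as in Section 4.1, would compare spirometry alone with control. The protocol states no separate effect for that contrast. The results of the two arms would also be exchanged in a report. Because all arms are planned at the same size, group counts would not expose the error. If this could easily happen, the trial's main comparison would be at risk.

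**Working it through.** **1. The two numberings side by side.**

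| Content | Section 4.1 | Section 8 |
|---|---|---|
| Spirometry only | arm 1 | arm 2 |
| Spirometry + telerehabilitation | arm 2 | arm 1 |
| Telerehabilitation only | arm 3 | arm 3 |
| Neither | control | control |

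Only arms 1 and 2 differ.

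**2. Which numbering the rest of the protocol uses.** Section 7.1.1 gives two rules: the device goes to arms 1 and 2, and rehabilitation goes to arms 2 and 3. Arm 2 is the only arm on both lists, so arm 2 is the combination. That leaves arm 1 as spirometry only and arm 3 as telerehabilitation only, exactly as in Section 4.1. The Section 8 numbering satisfies the device rule, since its arms 1 and 2 both use the spirometer. It fails the rehabilitation rule, since its arm 2 is spirometry only. The Visit 1 survey (arms 1 and 2) fits both numberings and decides nothing. Section 8 is therefore the outlier, and the intended code can be recovered from the protocol itself.

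**3. Whether the sized comparison can be misread.** In Section 8 each number is followed at once by the content of the arm. The assumed effect is also stated in words, for telerehabilitation with mobile spirometry. Number and description conflict only when set against Section 4.1. Within Section 8 the description leaves one reading: combination against control.

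**4. Whether any analysis depends on the number.** The Statistical Analysis text describes a paired comparison of clinic and home spirometry, regressions of compliance on clinical and spirometric variables, and correlations. None of these refers to an arm by number.

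**5. Whether any figure depends on the number.** The inputs, all from Section 8, are a control decline of 8.5%, a combination decline of 6%, SD 3%, 80% power and a 5% level (two-sided is assumed, as the text does not say). The difference is 8.5 − 6 = 2.5 points. With the normal approximation:

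n per group = 2 × (1.960 + 0.842)² × (3 / 2.5)² = 2 × 7.85 × 1.44 = 22.6, so 23 per group.

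A t-test calculation gives 24. The stated 46 per group is not reproduced; it equals 2 × 23, the total for two groups. At 46 per group the power is about 98% (97.9% by the normal approximation, 97.7% by t-test). That discrepancy is a different matter. What counts here is that no arm number enters the formula. The difference, the SD and the result are the same whether the combination is called arm 1 or arm 2.

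**6. Effect of exchanging the labels.** Before and after, every arm has 50 participants, with 45 expected after about 10% dropout (Section 1.1, Study Description). The total stays at 4 × 50 = 200, or 4 × 45 = 180 completers. The 2.5-point effect stays with the combination. Nothing else in the plan moves.

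**The case for a change.** The strongest case for a change is that this is a definite error in the text that sizes the trial. A SAP written from this protocol would inherit two conflicting codes, and equal arm sizes would hide a mix-up between two arms that together hold 2 × 50 = 100 of the 200 participants. Correcting two labels costs almost nothing, and a clause could be added to say that the stated 80% power and 5% level apply to the combination against control only.

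What stands is that the labels are wrong and that the right ones follow from Sections 4.1 and 7.1.1. The rest is weaker:

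- The mix-up requires a reader to skip the description printed beside each number and then to apply the bare number to another section's code. Nothing in the Statistical Analysis text leads there.
- The figure of 100 participants measures the size of the two arms. No participant's allocation, treatment or follow-up changes.
- The extra clause does not follow from a mislabel. It would restate an 80% power that the stated inputs do not give at 46 per group (about 98%, as worked above). The restriction to one contrast is also an inference. Section 8 speaks of groups with and without intervention and gives the same number to the other arms, and the primary objective in Section 3 covers the device, telerehabilitation, or both. What the trial is sized for in the single-component arms is a question of its own.

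**Conclusion.** The contradiction is real and clerical. Two labels in one paragraph of Section 8 are exchanged; arm 3 and control agree everywhere. The descriptions beside the numbers identify the sized comparison as spirometry plus telerehabilitation against control. Sections 4.1 and 7.1.1 fix the working code without ambiguity. No allocation, intervention, sample size, assumed effect or analysis depends on the Section 8 numbers, so the effect of the slip on the trial's results is nil and no change to the plan is called for. The labels can be tidied whenever the document is next edited.

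This rests on two assumptions. The first is that the allocation list and the data are coded as in Sections 4.1 and 7.1.1, which is the only code consistent with how the device and the training are handed out. The second is that whoever writes the analysis reads the arm descriptions as well as the numbers. The SAP is not available to confirm either, but an analyst would ordinarily meet both. The conclusion does not endorse the figure of 46 per group.
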